## 10.5 Baseline

Following subject enrollment, a baseline visit will be performed within 30 days. The baseline visit can be a standalone visit or occur on the same day as enrollment. The following procedures/data collection will be conducted during the baseline visit:

- Inclusion/exclusion criteria assessment
- Demographics
- Medical History
- Physical Exam

Version 4.0, 29-Apr-2022

Page 35 of 88

Medtronic

Form

- Medication Assessment
- Baseline 12-Lead ECG (within 60 days prior to enrollment)
- Baseline Echocardiography including LVEF and LVESV (within 60 days prior to enrollment)
- NYHA classification
- Adverse events (as applicable)
- Hospitalizations (as applicable)
- Death (as applicable)
- Study Deviations (as applicable)

### 10.6 CRT-D/CRT-P Implant

Following subject baseline, implant procedure of the CRT-D/CRT-P device will be performed within 30 days from subject enrollment. The implant procedure visit can be a standalone visit or occur on the same day as baseline. The following procedures/data collection will be conducted during the implant visit:

- Insertion procedure information
- ECG Belt application and data collection
- Lead Placement
- CSPOT Research System protocol
- CSPOT Chronic Final Device programming
- Initial and Final Device Interrogation (with either the initial or final being an interrogate ALL) and collection of .pdd file
- Fluoroscopic Images of final LBBP lead placement in RAO 30-45 degrees, LAO 30-45 degrees, and AP
- Adverse events (if applicable)
- Hospitalizations (if applicable)
- Death (if applicable)
- Device Deficiency (if applicable)
- System Modifications (if applicable)
- Study Deviations (if applicable)

### 10.6.1 CSPOT Acute Pacing Protocol

The CSPOT Acute Pacing Protocol and Medtronic CRT-D/CRT-P implant procedure must occur within 30 days of enrollment and will be performed in accordance with the Medtronic respective CRT-D/CRT-P implant instructions. The CSPOT pacing protocol should take place prior to the implant of the Medtronic CRT-D/CRT-P. During the CSPOT pacing protocol, two different sets of electrodes will be placed on the patient's chest: 1) a 12-lead surface ECG and 2) a multi-electrode ECG-belt.

# CSPOT (Conduction System Pacing Optimized
Therapy) Clinical Investigation PlanFormVersion 4.0, 29-Apr-2022Page 36 of 88Medtronic

Pacing leads (and defibrillation lead for CRT-D) will then be positioned as described in the CSPOT User Manual. Finally, a Millar pressure catheter will be introduced via the femoral artery retrograde across the aortic valve into the LV for hemodynamic pressure monitoring.

The different pacing configurations are depicted below and include univentricular (LVcs) pacing (CRT-P implants only), LVcs and RV pacing (CRT-D implants only), univentricular CSP (LBBP), and conduction system pacing optimized therapy (CSPOT) which is dual LV pacing of best LVcs and CSP. Different atrioventricular (AV) and intra-ventricular VV intervals will be evaluated. See figure 3 below for an overview.

[figure not shown]
[figure not shown]

Figure 3: Pacing Configurations

Version 4.0, 29-Apr-2022

Page 38 of 88

Form

#### 10.6.2 CSPOT Chronic Final Device Programming

After the acute pacing protocol, the patient is implanted with a CRT-P or CRT-D device, connected to the leads that were positioned during the acute study. For CRT-D patients, the pin for RV tip and ring will be capped. After the CRT device is implanted and the pocket is closed per standard of care, the device will be programmed to the CSPOT configuration that indicated the best optimization according to ECG Belt and/or physician discretion. This includes the SAV, PAV, and VV delay. The best LVcs electrode that was used during the acute testing will also be used for chronic programming unless phrenic nerve stimulation, lead dislodgement or high capture threshold occur. If the patient is not programmed to the CSPOT configuration, the subject must be exited from the study.

The chronic device programming includes:

Feature	Programmed Value
AdaptivCRT	Nonadaptive CRT
V-V pace delay	According to best result from ECG Belt during acute study and/or physician discretion
Paced AV	According to best result from ECG Belt during acute study and/or physician discretion
Sensed AV	Programmed to a value between (Paced AV – 30ms) and (Paced AV – 100ms), according to physician discretion.
LV pacing vector	Select the best LV cathode according to ECG Belt and/or physician discretion. Select anode according to physician discretion.
Multiple Point Pacing (MPP)	Off
RV Pace Polarity	Bipolar

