#### Table 5: CSPOT Research System Components

Model Number(s)	Component	Manufacturer	Investigational or Market- released
EA1B5S, EA1B5L (Belt) EA1A (amplifier) EA1T (tablet)	ECG Belt System	Medtronic	Investigational
825-0101	Millar Pressure Catheter	Millar	Market-Released
850-5148	Millar Connection Cable	Millar	US: Investigational OUS: Market-Released
00EPT01	Cardiotek EP-Tracer 38 System	Cardiotek	Market-Released
N/A	Threshold Cable	Any manufacturer	Market-Released
5392	Medtronic External Pacer	Medtronic	Market-Released
3830 SelectSecure	Medtronic Pacing Leads	Medtronic	Investigational when used in the study (due to implant location)
LV Quad polar leads: 4298, 4398, 4598 (Attain Performa)	Medtronic Pacing Leads	Medtronic	Market-Released
4798 (Attain Stability)			
N/A	RA bipolar lead	Any manufacturer	Market-Released
RV defibrillation lead with IS1/DF1 connector:	Medtronic Defibrillation Leads	Medtronic	Market-Released
6935 (Sprint Quattro single coil)			
6947 (Sprint Quattro dual coil)			
CRT P Quad and CRT-D Quad w/DF-1 Connector Models (see Table 4)	Medtronic CRT devices	Medtronic	Market-Released

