### 10.7.2 Study Exit

At the completion of the 6-month follow-up visit, subjects will be exited from the study. The 6-month follow-up visit and exit visit should be combined and both a 6-month follow-up CRF and a Study Exit CRF need to be completed.

Prior to exiting a subject from the study, it is recommended to follow the subject until all ongoing AEs are resolved or unresolved with no further actions planned. Following exit, subjects will continue to receive standard medical care. Upon exiting from the study, no further study data will be collected, or study visits will occur for the subject. All data available through the time of the subject's exit will be used for analysis. Subjects who are exited from the study prior to the 6 months visit will not be replaced with another enrolled subject.

Subjects are urged to remain in the study as long as possible but may be exited from the study for any of the following situations:

• Study completion or termination

Page 41 of 88

Medtronic

- Subject lost to follow-up
- CRT-D/CRT-P device explanted and not replaced
- Implant attempt, however, no CRT-D/CRT-P was implanted

Version 4.0, 29-Apr-2022

- Subject has an invasive system modification that has intent to change the pacing behavior from the acute system configuration settings
- The following occurs during the lead positioning in the acute protocol testing:
  - Unable to place the LBBP lead
  - Unable to place the LV lead through the CS
  - Subject has a sustained sinus rate > 110 BPM
  - Subject has sustained AV block, AF, or SVT
- Subject death
- Subject did not meet inclusion/exclusion criteria
- Subject was not implanted with a Medtronic CRT-D/CRT-D device
- Subject did not provide consent or data use protection authorization
- Subject chooses to withdraw (e.g., consent withdrawal, relocation to another geographic location)
- Investigator deems withdrawal necessary (e.g., medically justified, inclusion/exclusion criteria not met, failure of subject to maintain adequate study compliance)

The following information/procedure is to be collected/performed at study exit:

- Date of Exit
- Reason for Exit
- Initial and Final Device Interrogation (with either the initial or final being an interrogate ALL) and collection of .pdd file
- Adverse Event Collection
- Device deficiencies
- Study deviations

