### 10.7.5 Investigator Withdraws Subject

No subject should be withdrawn by investigators unless compelling medical justification is present. It is recommended investigators discuss any withdrawals with the study team prior to withdrawing subjects. If an Investigator Withdrawal is necessary, the following data should be collected prior to subject withdrawal if possible:

- Reason for investigator withdrawal from the study
- All ongoing AEs are resolved or unresolved with no further actions planned

In the event of subject relocation, it is recommended to contact the study team to attempt to transfer the subject to another investigational site and retain the subject in the study.

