### **11.2 Risk Minimization**

The potential risks associated with the CSPOT Research System were identified and have been mitigated; see Table 9 below. Any potential risks associated with this study are further minimized by selecting qualified investigators and training study personnel on the CIP.

In addition, investigators will be actively involved in the implantation and follow-up of the subjects implanted with the CRT-D/CRT-P device.

CSPOT (Conduction System Pacing Optimized Therapy) Clinical Investigation Plan		Form
Version 4.0, 29-Apr-2022 Page 48 of 88		Medtronic
Version 4.0, 29-Apr-2022 Page 48 01 88		meanorme

Risks will be minimized by careful assessment of each subject prior to, during, and after implant of the CRT-D/CRT-P device. Prior to implant, it is recommended subjects undergo a complete physical evaluation.

Medtronic has further minimized the possibility of risks by performing required laboratory and preclinical testing prior to the CSPOT study, implementing quality control measures into production processes, providing guidelines for subject selection and evaluation, and providing adequate instructions and labeling.

After implantation, subjects in the CSPOT study will be followed for 6 months to monitor the condition of the implanted system. At each protocol required follow-up, the investigator must interrogate the CRT-D/CRT-P to verify appropriate function and to evaluate pacing and sensing characteristics and to assess any adverse events.

Potential risk	Risk Minimization
Precursor to infection	• CSPOT research system design verification ensuring intended use in the sterile field - including the leads, Millar LV pressure
Associated AEs: Infection, Cardiac inflammation, Discomfort, Fever	catheter, and lead cables/pocket clip are all provided in sterile packaging
	
 
CSPOT research system design verification ensuring reusable components can be re-sterilized – including IFU instructions on re-sterilization (if applicable)
 

	
 
Instruction provided in IFU for implant procedure; specifically, for the placement of leads, set-up of Millar LV pressure catheter, and appropriate pacing protocol/configuration
 

Precursor to acute tissue/vascular	CSPOT research system design verification ensuring
trauma	

compliance to EN 60601-1:2006/A1:2013

Instruction provided in IFU for implant procedure; specifically,

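### Implanted subjects not programmed to CSPOT must leave the study, so adverse events and device deficiencies that begin after exit go uncaptured, at odds with the 6-month follow-up offered as a risk control

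*Protocol*

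**What the plan says.** Protocol 10.6.2 sets the order of events. After the acute protocol the patient receives a CRT device "connected to the leads that were positioned during the acute study". Once the pocket is closed, "the device will be programmed to the CSPOT configuration that indicated the best optimization according to ECG Belt and/or physician discretion". The section then adds: "If the patient is not programmed to the CSPOT configuration, the subject must be exited from the study".

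Protocol Table 5 lists the 3830 lead as investigational in this study because of where it is placed. Protocol 10.7.2 gives the consequence of exit: "Upon exiting from the study, no further study data will be collected, or study visits will occur for the subject". Protocol 10.11 ties adverse-event collection to the period of the subject's participation.

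Protocol 11.2, on risk minimization, says that after implantation "subjects in the CSPOT study will be followed for 6 months to monitor the condition of the implanted system".

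Protocol 10.7.2 also lists the situations in which a subject may be exited. Being programmed to something other than CSPOT is not named there.

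**The concern.** The risk control in 11.2 is about the implanted system, not the pacing mode. A subject programmed to another mode carries the same hardware: no section calls for the 3830 lead to be removed when CSPOT is not programmed. Protocol 11.1 names risks of placing that lead (right bundle branch block, tricuspid valve damage, septal perforation) and states that MRI-conditional labeling does not apply to these lead configurations. None of that depends on the mode programmed.

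What is at stake is safety information from a small feasibility study. Safety of the system is part of the stated purpose (Synopsis), the Research System has had no previous clinical study use (18.7.1), and there is no data monitoring committee (18.5). Each implanted subject's follow-up therefore carries weight.

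**Working it through.** The plan states no figure to reproduce, since the maximum of 60 is set by logistics (Protocol 14.8). The check is mainly a reading of the sections against one another.

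**Step 1. Is the hardware in place when the rule applies?** Yes. In 10.6.2, implant, lead connection and pocket closure precede programming. That the lead then stays in place is an inference, but no text points the other way.

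**Step 2. What is collected after exit?**
- 10.7.2: no study data and no visits after exit. Before exit, "it is recommended to follow the subject until all ongoing AEs are resolved or unresolved with no further actions planned". This is a recommendation and concerns events already present.
- 12.3: after an early exit, efforts should be made to follow events to resolution. The section deals with updates to events already reported.
- 12.5.1.1: follow-up of a reported event ends at resolution, exit or study closure, whichever is first.
- 10.7.2, closing sentence: follow-up for safety outside the investigation may be requested, but only if discontinuation was for safety or lack of effectiveness.
- 12.7: product complaint reporting exists, but is expressly not part of the study.

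None of these captures, as study data, an adverse event or device deficiency that begins after exit.

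**Step 3. Do the exit provisions agree?** 10.6.2 is mandatory. The 10.7.2 list is permissive and omits this reason. 11.2 describes 6 months of follow-up after implantation and makes no exception for programming.

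**Step 4. How large could the loss be?** Let d be the fraction exited under this rule. The documents do not give d, so 5-15% is an assumption. The base of 60 is maximum enrollment, not implants, so the counts are upper values for each d.
- Subjects exited: k = 60d
- Subject-months lost, if exit closely follows implant: 6k, out of 60 × 6 = 360
- One-sided 95% upper limit if no events are seen: 1 − 0.05^(1/(60 − k))
- Chance of seeing at least one late event at an assumed true risk of 2%: 1 − 0.98^(60 − k)

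| d | k | Subject-months lost | Upper limit, zero events | Chance of at least one event |
|---|---|---|---|---|
| 0% | 0 | 0 | 4.9% | 70.2% |
| 5% | 3 | 18 | 5.1% | 68.4% |
| 10% | 6 | 36 | 5.4% | 66.4% |
| 15% | 9 | 54 | 5.7% | 64.3% |

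The loss of precision is modest. It is zero if nobody is exited under the rule.

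**The case against.** The strongest reply is that this is a defined exit in a study of CSPOT pacing, that early exits always qualify a general statement such as the one in 11.2, and that the protocol asks for events to be followed before and after exit. Part of this stands. The safeguards in 10.7.2 and 12.3 are real, and 10.6.2 sets no exit date, so it would be wrong to say that all safety follow-up stops on the day of implant. The gap is limited to events and deficiencies with new onset after exit. It remains a gap, because the early-exit safeguards do not reach those events and the subject still has the system that 11.2 says will be monitored.

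A reader might draw three stronger conclusions that the documents do not support.

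- *That 10.6.2 contradicts 10.7.5.* The latter says "No subject should be withdrawn by investigators unless compelling medical justification is present". It governs discretionary withdrawal by investigators. An exit that the protocol itself requires does not breach it.
- *That the 6-month LVEF, LVESV and Clinical Composite Score results are biased by the rule.* Secondary objectives 3-5 ask about the chronic response to CSPOT pacing, so a summary in subjects paced that way answers the stated question. The restriction to completers or observed scores is stated openly in Protocol 14.5.3-14.5.5, and SAP 7.1.1 plans a flow diagram and a summary of exits by reason. Those results cannot be read as the outcome of everyone implanted, but the plan does not claim that. Any figure for a shift in mean LVEF change would need an exit rate and a response in exited subjects, and the documents supply neither.
- *That the rule removes subjects in whom CSPOT was found unsuitable.* Phrenic nerve stimulation, dislodgement and high threshold appear in 10.6.2 as grounds for using a different LV electrode, not for leaving CSPOT. The exit may seldom be triggered.

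**Conclusion.** The point holds as a gap in safety collection and a mismatch between sections. Protocol 10.6.2 requires exit of subjects who already have the study system implanted, 10.7.2 then ends study data, and new-onset adverse events and device deficiencies are lost. This does not fit the purpose of follow-up given in 11.2, and the exit list in 10.7.2 does not contain the reason.

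The size is unknown. At an assumed 5-15% of 60, it is 3-9 subjects and up to 18-54 of 360 subject-months; it could be none. The conclusion rests on the lead remaining in place after exit, which follows from the sequence in 10.6.2 but is not stated.

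The acute primary objectives are not affected. They use data taken at implant (Protocol 14.4), data up to exit are retained (10.7.2), and the Analysis Cohort may include subjects without a 6-month visit (Protocol 14.1, SAP 7.1.3).

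**What to change.** Reconcile Protocol 10.6.2, 10.7.2 and 11.2:

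- Keep implanted subjects who are not programmed to CSPOT in the study for adverse-event and device-deficiency collection through 6 months, flagged as not on CSPOT.
- Bring the 10.7.2 list and the 10.6.2 rule into line, so that one statement governs.
- Keep the LVEF, LVESV and Clinical Composite Score summaries in CSPOT-programmed subjects as the main analysis, and say so in 14.5.3-14.5.5. Otherwise a retained subject who attends the 6-month visit could enter them under the present inclusion wording.
- Report beside those summaries the number of subjects not programmed to CSPOT and the reasons.

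The cost is amendment wording and follow-up contact for a few subjects at most. No change to device programming is proposed.

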#### Table 7: Device programming during chronic follow up.

Version 4.0, 29-Apr-2022

Page 39 of 88

Μ	_				
		r r		n	
	u		0		

Form

Rate Adaptive AV	On
Pace Amplitudes and Pulse Widths	Automatic capture management recommended
All other device parameters	According to physician discretion

### **10.7 Scheduled Follow-up Visits**

A scheduled visit will occur at 6 months post implant. Should a subject miss the visit or the visit fall outside the pre-specified window, a study deviation must be reported. A late visit is preferred over a missed visit but must be accompanied by a deviation. The table below indicates the follow up visit windows.

Visit	Window (days post enrollment)			
	Open	Target	Close	
Baseline	0	15	30	
Visit		Window (days post enrollment)		
	Open	Target	Close	
Implant	0	15	30	
Visit	Window (days post implant)			
	Open	Target	Close	
6-Month Follow Up	150	180	210	

Version 4.0, 29-Apr-2022

Page 40 of 88

Form

### 10.7.1 6-Month In-Office Follow Up Visit

An in-office follow-up visit will be completed at 6 months post device insertion to collect chronic data from the CSPOT system.

The following information is required to be collected at the **6-Month** scheduled follow-up visit:

- Physical Exam
- Medications Assessment
- NYHA Classification
- Patient Global Assessment
- 6-Month 12 lead ECG (within 30 days prior to visit date)
- 6-Month Echocardiography including LVEF and LVESV (within 30 days prior to visit date)
- Final Device Programming
- Initial and Final Device Interrogation (with either the initial or final being an interrogate ALL) and collection of .pdd file
- Adverse events (if applicable)
- Hospitalizations (if applicable)
- Device Deficiencies (if applicable)
- Study Deviations (if applicable)
- System Modifications (if applicable)
- Death (if applicable)

### 10.7.1.1 Final Device Programming

After the 6-month follow up visit procedures are completed, the subject's device will be programmed per physician discretion. A final device interrogation and collection of .pdd file is required to capture final device settings.

### 10.7.2 Study Exit

At the completion of the 6-month follow-up visit, subjects will be exited from the study. The 6-month follow-up visit and exit visit should be combined and both a 6-month follow-up CRF and a Study Exit CRF need to be completed.

Prior to exiting a subject from the study, it is recommended to follow the subject until all ongoing AEs are resolved or unresolved with no further actions planned. Following exit, subjects will continue to receive standard medical care. Upon exiting from the study, no further study data will be collected, or study visits will occur for the subject. All data available through the time of the subject's exit will be used for analysis. Subjects who are exited from the study prior to the 6 months visit will not be replaced with another enrolled subject.

Subjects are urged to remain in the study as long as possible but may be exited from the study for any of the following situations:

• Study completion or termination

Page 41 of 88

Medtronic

- Subject lost to follow-up
- CRT-D/CRT-P device explanted and not replaced
- Implant attempt, however, no CRT-D/CRT-P was implanted

Version 4.0, 29-Apr-2022

- Subject has an invasive system modification that has intent to change the pacing behavior from the acute system configuration settings
- The following occurs during the lead positioning in the acute protocol testing:
  - Unable to place the LBBP lead
  - Unable to place the LV lead through the CS
  - Subject has a sustained sinus rate > 110 BPM
  - Subject has sustained AV block, AF, or SVT
- Subject death
- Subject did not meet inclusion/exclusion criteria
- Subject was not implanted with a Medtronic CRT-D/CRT-D device
- Subject did not provide consent or data use protection authorization
- Subject chooses to withdraw (e.g., consent withdrawal, relocation to another geographic location)
- Investigator deems withdrawal necessary (e.g., medically justified, inclusion/exclusion criteria not met, failure of subject to maintain adequate study compliance)

The following information/procedure is to be collected/performed at study exit:

- Date of Exit
- Reason for Exit
- Initial and Final Device Interrogation (with either the initial or final being an interrogate ALL) and collection of .pdd file
- Adverse Event Collection
- Device deficiencies
- Study deviations

If discontinuation is because of safety or lack of effectiveness, the subject may be asked to be followed for collecting safety data outside the clinical investigation.

